6.7.3. Reoperation Surgery

For analysis of the time to the reoperation, the Kaplan-Meier method will be used. The times between surgery and the most recent or last available assessment per subject will be used together with the times between surgery and the date of reoperation (earliest reoperation in case that one subject experienced more than one reoperation). This analysis is part of the final report.

Evaluation Variable / Question	Level of Measurement	Recode and Analysis Plan
Adverse Events / Reoperation Surgery		
Creation of variable Difference between Date of Surgery [dd.mm.yyyy] and Date of First Reoperation [dd.mm.yyyy] in days (Variable(s): VISITDT)	Quantitative, ratio	Case summary with number and percentage of valid cases/values, missing cases/values (if any) and total cases/values. Mean, median, interquartile range, maximum, minimum, standard deviation, 95% confidence interval for mean, Shapiro-Wilk Test.
Creation of variable Difference between Date of Surgery [dd.mm.yyyy] and Date of “most recent” Visit [dd.mm.yyyy] in days (Variable(s): VISITDT)	Quantitative, ratio	N/A (Analyzed above), used for survivorship
Create new variable “Grouping variable – First Reoperation” (Variable(s): VISITDT)	Qualitative, nominal	- censored = survivors - events = first (earliest) Reoperation
Create new variable “Combined Time – First Reoperation” (Variable(s): VISITDT)	Quantitative, ratio	- Use time between surgery and most recent visit for surviving subjects - Use time between surgery and first reoperation for subjects with reoperation(s)
Use variables “Combined Time – First Reoperation” and “Grouping variable – First Reoperation”	Qualitative, nominal Quantitative, ratio	Case summary with number and percentage of valid cases/values, missing cases/values (if any) and total cases/values. Kaplan-Meier survival analysis: subject ID, time, status, cumulative proportion, Kaplan-Meier estimate, standard error of KM estimate, number of cumulative events, number of remaining cases, mean for survival time with 95% confidence interval, survival graph, hazard graph.

Table 6.7.3: All Assessments – Revision Surgery Tables List

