#### 8.3. SECONDARY ENDPOINTS (FOR BOTH ARM A AND B)

In addition to the principal endpoint, information on the following outcomes will be assessed up to 10 years after the index procedure:

- Safety: Incidence of device-related intraoperative and postoperative AEs
- Efficacy/Performance: Implant survivorship will be monitored

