### 11.3.3. Secondary Endpoints

The incidence of device-related AEs and implant survivorship will be assessed up to ten years after the index procedure and monitored through collection and analyses. These analyses will be part of the annual and final reports.

Furthermore, time to (earliest) device-related AEs will be analyzed as well. For analysis of the time to the (earliest) device-related AEs as well as the time to secondary procedure (revision, removal, reoperation), the Kaplan-Meier method will be used. The time between surgery and the last available assessment will be used together with the time between date of surgery and the date of secondary procedure. Considered variables, the level of measurement and the planned analysis steps are listed in detail in the SAP.

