3.1.2. Secondary Analyses

The incidence of device-related AEs and implant survivorship will be assessed up to ten years after the index procedure and monitored through collection and analyses.

Furthermore, time to (earliest) device-related AEs will be analyzed as well. For analysis of the time to the (earliest) device-related AEs as well as the time to secondary procedure (revision, removal, reoperation), the Kaplan-Meier method will be used. Considered variables, the level of measurement and the planned analysis steps are listed in detail in the SAP. These analyses will be part of the final report.

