6.6. ANALYSIS OF CI ENDPOINTS

Evaluation Variable / Question	Level of Measurement	Analysis Plan	Inclusion		
Endpoints – Primary Endpoint Arm A (TSA/HA)			IR	FR	N/A
Use variable Total ASES Score 24 Months [points]:					
Based on the underlying distribution of the data and the result of the normality assessment, either the parametric one-sample t-test or the non-parametric one-sample sign test will be used to compare the 24 months postoperative ASES Shoulder Score results of the ReUnion RFX System (TSA/HA) against the value of 38.41 points.				X	
The analysis of the primary endpoint will be part of the final report					
Endpoints – Primary Endpoint Arm B (RSA)			IR	FR	N/A
Use variable Total ASES Score 24 Months [points]:					
Based on the underlying distribution of the data and the result of the normality assessment, either the parametric one-sample t-test or the non-parametric one-sample sign test will be used to compare the 24 months postoperative ASES Shoulder Score results of the ReUnion RFX System (RSA) against the value of 63.40 points.				X	
The analysis of the primary endpoint will be part of the final report.					

Table 6.6.1: Endpoints – Primary Endpoint Tables List

Evaluation Variable / Question	Level of Measurement	Recode and Analysis Plan	Inclusion		
			IR	FR	N/A
Adverse Events – Time to (earliest) Device Related Adverse Event / Incident					
Creation of variable Difference between Date of Surgery [dd.mm.yyyy] and Date of First Device Related Adverse Event [dd.mm.yyyy] in days  (Variable(s): VISITDT; AEONSTDT)	Quantitative, ratio	Case summary with number and percentage of valid cases/values, missing cases/values (if any) and total cases/values. Mean, median, interquartile range, maximum, minimum, standard deviation, 95% confidence interval for mean, Shapiro-Wilk Test.		X	
Creation of variable Difference between Date of Surgery [dd.mm.yyyy] and Date of “most recent” Visit [dd.mm.yyyy] in days  (Variable(s): VISITDT)	Quantitative, ratio	N/A (Analyzed above), used for survivorship		X	
Create new variable “Grouping variable – First Device Related Adverse Event” (Variable(s): AEONSTDT)	Qualitative, nominal	- censored = survivors - events = first (earliest) Device Related Adverse Event		X	

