Create new variable “Combined Time – First Device Related Adverse Event” (Variable(s): AEONSTDT)	Quantitative, ratio	- Use time between surgery and “most recent” visit for surviving subjects - Use time between surgery and first device related adverse event for subjects with device related adverse event		X	
Use variables “Combined Time – First Device Related Adverse Event” and “Grouping variable – First Device Related Adverse Event”	Qualitative, nominal Quantitative, ratio	Case summary with number and percentage of valid cases/values, missing cases/values (if any) and total cases/values. Kaplan-Meier survival analysis: subject ID, time, status, cumulative proportion, Kaplan-Meier estimate, standard error of KM estimate, number of cumulative events, number of remaining cases, mean for survival time with 95% confidence interval, survival graph, hazard graph.		X	

Table 6.6.2: Endpoints – Secondary Endpoint Time to (earliest) Device Related Adverse Event / Incident Tables List

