6.7.2. Mortality

For analysis of the time to death or mortality, the Kaplan-Meier method will be used. The times between surgery and the most recent or last available assessment per subject will be used together with the times between surgery and the date of death. This analysis is part of the final report.

Evaluation Variable / Question	Level of Measurement	Recode and Analysis Plan
All Assessments - Mortality		
Creation of variable Difference between Date of Surgery [dd.mm.yyyy] and Date of Death [dd.mm.yyyy] in days  (Variable(s): VISITDT; DOSEDD)	Quantitative, ratio	Case summary with number and percentage of valid cases/values, missing cases/values (if any) and total cases/values. Mean, median, interquartile range, maximum, minimum, standard deviation, 95% confidence interval for mean, Shapiro-Wilk Test.
Creation of variable Difference between Date of Surgery [dd.mm.yyyy]	Quantitative, ratio	N/A (Analyzed above), used for survivorship

and Date of “most recent” Visit [dd.mm.yyyy] in days (Variable(s): VISITDT)		
Create new variable “Grouping variable - Mortality” (Variable(s): PRIMRSN)	Qualitative, nominal	- censored = survivors - events = death
Create new variable “Combined Time - Mortality” (Variable(s): VISITDT; DOSEDD)	Quantitative, ratio	- Use time between surgery and most recent visit for surviving subjects - Use time between surgery and death for deceased subject
Use variables “Combined Time - Mortality” and “Grouping variable - Mortality”	Qualitative, nominal Quantitative, ratio	Case summary with number and percentage of valid cases/values, missing cases/values (if any) and total cases/values. Kaplan-Meier survival analysis: subject ID, time, status, cumulative proportion, Kaplan-Meier estimate, standard error of KM estimate, number of cumulative events, number of remaining cases, mean for survival time with 95% confidence interval, survival graph, hazard graph.

Table 6.7.2.: All Assessments – Mortality Tables List

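### No planned analysis estimates the 10-year incidence of device-related adverse events well: crude proportions run low under drop-out, and two-state Kaplan-Meier would run high if its complement were read as incidence

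*SAP*

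**What the plan says.** Protocol 8.3 lists two secondary endpoints: "Safety: Incidence of device-related intraoperative and postoperative AEs" and "Efficacy/Performance: Implant survivorship will be monitored". SAP 3.1.2 sets the horizon: "The incidence of device-related AEs and implant survivorship will be assessed up to ten years after the index procedure".

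The SAP plans these analyses:

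- **SAP 6.1, Table 6.1.1.** Device-related events are summarised as frequencies and proportions. No time horizon is given, and nothing is said about subjects who leave early.
- **SAP 6.6, Table 6.6.2.** This Kaplan-Meier analysis of the first device-related event is captioned as a secondary endpoint. Its status variable has two values: "censored = survivors - events = first (earliest) Device Related Adverse Event". Its time variable has two rules. Subjects with an event follow "Use time between surgery and first device related adverse event for subjects with device related adverse event"; surviving subjects get the time to their latest visit.
- **SAP 6.7.3.** The Kaplan-Meier analysis of first reoperation has the same structure, with "Use time between surgery and most recent visit for surviving subjects".
- **SAP 6.7.2.** Only the mortality analysis has a rule for the dead: "Use time between surgery and death for deceased subject". It uses PRIMRSN for status and DOSEDD for the date of death.

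Protocol 11.3.3 presents Kaplan-Meier as an addition to the incidence: "Furthermore, time to (earliest) device-related AEs will be analyzed as well". Protocol 9.3 says that a death does not count as a device failure unless the device caused it or it is attributable to the device. Neither document mentions competing risks.

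**The concern.** Incidence over 10 years means the share of implanted subjects who have a device-related event within 10 years, in a population where some die first. Neither planned summary estimates that share.

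A crude proportion counts a subject who left in year 3 as event-free for all 10 years, so it is too low. Kaplan-Meier with deaths censored treats the dead as if they could still have the event, so 1-KM answers what the risk would be if nobody died, which is higher. The gap widens with follow-up.

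At stake is the long-term safety figure of a post-market study. A reader of the final report would find a crude percentage and a Kaplan-Meier curve that disagree, with no statement of which one is the endpoint. There is also a gap in the rules: read literally, a subject who dies event-free is neither a survivor nor an event, and so has no time in Table 6.6.2 or in 6.7.3.

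**Working it through.** The documents state no incidence, survivorship, mortality or event rate, so there is no figure of theirs to reproduce. The check below is an illustration.

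**Inputs**

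- Horizon T = 10 years (Protocol 8.3, SAP 3.1.2).
- Overall drop-out 56% (SAP 3.2.1 and 3.2.2), taken here as applying to 10 years. The source cited for it is a follow-up study of at least 10 years. The split into death and other loss is not given.
- Assumed: 10-year risk in the absence of death R = 10%, which is what 1-KM targets; 10-year mortality M = 10% to 50%; events, death and other loss independent; constant hazards unless stated.

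**1-KM against cumulative incidence**

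The event hazard is r = -ln(1-R)/T = -ln(0.90)/10 = 0.01054 per year. The death hazard is m = -ln(1-M)/T. The cumulative incidence is CIF = r/(r+m) × [1 - (1-R)(1-M)].

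Example with M = 30%: m = 0.03567, so CIF = 0.01054/0.04620 × (1 - 0.90 × 0.70) = 0.2280 × 0.37 = 8.4%. The ratio is 10/8.44 = 1.19.

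| Assumed 10-year mortality | 1-KM | CIF | Excess (points) | Ratio |
|---|---|---|---|---|
| 10% | 10% | 9.5% | 0.5 | 1.05 |
| 20% | 10% | 9.0% | 1.0 | 1.11 |
| 30% | 10% | 8.4% | 1.6 | 1.19 |
| 40% | 10% | 7.9% | 2.1 | 1.27 |
| 50% | 10% | 7.3% | 2.7 | 1.38 |

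If two thirds of the cumulative event hazard falls in years 0 to 2, the ratio for mortality of 20% to 50% drops to 1.06 to 1.18. This case deserves weight, because the endpoint includes intraoperative events, which precede any later death.

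**Crude proportion against cumulative incidence**

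Take enrolled subjects as the denominator and assume that events after drop-out go unseen. The total attrition hazard is a = -ln(1-0.56)/10 = 0.08210. The expected crude proportion is r/(r+a) × [1 - 0.90 × 0.44] = 0.1137 × 0.604 = 6.9%, however the 56% is split. The CIF is 9.0%, 8.4% or 7.9% at mortality of 20%, 30% or 40%, so the crude figure is 1.0 to 2.1 points too low. The shortfall vanishes only if all the drop-out is death.

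**Simulation**

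Death of 20%, 30% or 40% was combined with other loss of 45%, 37.1% or 26.7%, each pair giving about 56% in total; for example, 1 - 0.80 × 0.55 = 0.56. Event-free subjects were censored at their last scheduled visit for 1-KM. Means for n = 100, with 2,000 replicates per case:

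| Mortality | 1-KM | Aalen-Johansen | Crude |
|---|---|---|---|
| 20% | 10.3% | 8.9% | 6.8% |
| 30% | 10.4% | 8.5% | 6.9% |
| 40% | 10.3% | 7.8% | 6.8% |

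The two planned summaries fall on either side of the target. The standard deviation of 1-KM is about 3.9 points at n = 100 and 5.5 points at n = 50.

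**The case against.** A reader might infer that the plan will report an incidence biased upward because it censors deaths. The documents do not support that. Neither says that 1-KM is the incidence; the listed output is the survival estimate with its graphs, and Kaplan-Meier is added to the tabulated proportions. The proportions err in the opposite direction. Censoring of deaths is also an inference: what the text shows is a missing rule. It is a strong inference, because the text of 6.7.3 uses each subject's last available assessment and only two states exist.

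A reader might also infer that the reoperation analysis in 6.7.3 is wrong. It is not. Reoperation bears on implant survivorship, and Kaplan-Meier with deaths censored is a legitimate estimate of net survivorship if death is independent of the event. It also agrees with Protocol 9.3, except for device-attributable deaths, which two-state coding cannot express.

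Finally, the size rests wholly on assumed mortality. A figure near the top of the range would make almost all of the 56% drop-out death, and other loss does not create the Kaplan-Meier gap. Sampling error in a study of 100 subjects, analysed by arm, exceeds the gap.

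All of this stands and limits the point. It does not remove it: Table 6.6.2 is captioned as a secondary endpoint, the named target is incidence, and a confidence interval shows sampling error but not this bias.

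**Conclusion.** The point holds as a minor improvement. The plan names a 10-year incidence and offers no estimator that targets it under both death and other loss. The directions follow from the methods: crude proportions are low when subjects are lost for reasons other than death, and 1-KM is high when read as incidence and event-free deaths are censored. The size is illustrative only. For a 1-KM of 10%, the ratio to the cumulative incidence is about 1.05 to 1.38 over assumed mortality of 10% to 50% with constant hazards, and it is smaller with early events. For reoperation, what is missing is a label and a rule for deaths. These analyses carry no test or threshold, so the primary conclusion is unaffected.

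**What to change.** 1. **SAP Table 6.6.2.** Add a third status code for death without a prior device-related event, taken from PRIMRSN, with time from surgery to death from DOSEDD. Report the Aalen-Johansen cumulative incidence by arm, with death as the competing event and a 95% confidence interval, as the 10-year incidence of device-related adverse events.
2. **SAP 6.1.** Keep the crude tables as counts of observed events, and say that they are not the 10-year incidence estimate.
3. **SAP 6.7.3.** Keep Kaplan-Meier and label it net implant survivorship. State the status and time for subjects who die without reoperation. A cumulative incidence curve beside it is optional.
4. **Device-attributable deaths.** Reconcile their coding in both analyses with Protocol 9.3.

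The cost is one extra code and one table per endpoint. SPSS may need to be supplemented by another package, and SAP 4.5 already allows other standard software. The death data are already planned for SAP 6.7.2. SAP 3.1.2 and 6.7.3 place the time-to-event analyses in the final report, so the rule can be set before they are run.

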6.7.4. ASES Total Score – Within subject changes by visit

The within subject score changes of the total ASES Shoulder Score from visit to visit will be analyzed to help identifying the changes on the subject level. This analysis is part of the final report.

The within subject changes by visit of the ASES Shoulder Score must compare all follow-up visits against each other (m x n) in accordance to table 6.7.4.1 and the analysis tables in this chapter.

		ASES Shoulder Score – Follow-up Visits to be compared												
		Follow-up Visits (n)												
Comparison		Preop	6 Weeks	6 Months	12 Months	24 Months	36 Months	48 Months	60 Months	72 Months	84 Months	96 Months	108 Months	120 Months
		Follow-up Visits B (m)	Preop											
6 Weeks	x													
6 Months	x		x											
12 Months	x		x	x										
24 Months	x		x	x	x									
36 Months	x		x	x	x	x								
48 Months	x		x	x	x	x	x							
60 Months	x		x	x	x	x	x	x						
72 Months	x		x	x	x	x	x	x	x					
84 Months	x		x	x	x	x	x	x	x	x				
96 Months	x		x	x	x	x	x	x	x	x	x			
108 Months	x		x	x	x	x	x	x	x	x	x	x		
120 Months	x		x	x	x	x	x	x	x	x	x	x	x	

*All combinations marked with an "x" must be performed

Table 6.7.4.1: All Assessments – ASES Shoulder Score – Follow-up Visits to be compared

Evaluation Variable / Question	Level of Measurement	Recode and Analysis Plan
All Assessments - ASES Shoulder Score Within Subject Changes		
Creation of variable “ASES Total Score change between m visit and n [points]” Difference between “ASES Total Score m [points]” with “ASES Total Score n [points]” (Variable(s): FINSCORE)	Quantitative, ratio	Calculate difference (could be negative or positive). Case summary with number and percentage of valid cases/values, missing cases/values (if any) and total cases/values. Mean, median, interquartile range, maximum, minimum, standard deviation, 95% confidence interval for mean, Shapiro-Wilk Test.

Table 6.7.4.2: All Assessments – ASES Total Score Within Subject Changes

7. Table Templates (Tables, Figures, Listings - TFL)

Tables must consist of at least a headline, the variable/analysis-object label and column headers. Furthermore, the table headline must contain the “Analysis Section”(e.g. Demographics, Operative) the variable label (e.g. Gender, Age) as well as the table type (Frequencies, Listing). If the table is referring to a subgroup, a notification must be entered in the headline as well. Figures (if any) must be clearly labeled and numbered by a figure number and title in addition to the axis and category labeling created by software packages (e.g. IBM SPSS).

7.1. FREQUENCIES

All answered response options must be listed with the appropriate label, other response options do not have to be displayed necessarily. In the event of missing answers, the frequencies must be included in an extra row as well (“Missing”). All given answers must be added up in an extra row (“Total”). In addition to the number of frequencies, percentages must be displayed in a separate column. Each analysis arm must be displayed separately, as well as a overall result of both arms has to be created. The two arms and the overall results can be combined in one table or in three separate tables.

“Analysis Section” – “Variable Label” – Frequencies

Characteristic		ARM A		ARM B		Total	
		n	%	n	%	n	%
“Variable Label”	“Response A”	“xxx”	“xxx”	“xxx”	“xxx”	“xxx”	“xxx”
	“Response B”	“xxx”	“xxx”	“xxx”	“xxx”	“xxx”	“xxx”
	Missing	“xxx”	“xxx”	“xxx”	“xxx”	“xxx”	“xxx”
	Total	“xxx”	“xxx”	“xxx”	“xxx”	“xxx”	“xxx”

Table 7.1.1: Frequencies Table Template

If multiple subgroups/clusters (e.g. Sites, Visits) should be displayed in one table, an extra column (“Group X”) and/or extra rows (“Group Y”) must be added. Same applies to (sub-) questions, which can be merged in one table. It is recommended to add an extra “Total” column and row, for adding up the subgroups, if possible, from a statistical point of view. In addition, subgroups must be named in the headline as well (“by Group X and by Group Y”).

“Analysis Section” – “Variable Label” – Frequencies – by “Group X” and “Group Y”

Characteristic		“Group X1”						“Group X2”						Total	
		Arm A		Arm B		Total “G X1”		Arm A		Arm B		Total “G X2”			
		n	%	n	%	n	%	n	%	n	%	n	%		
“Group Y1”	“Response A”	“xxx”	“xxx”	“xxx”	“xxx”	“xxx”	“xxx”	“xxx”	“xxx”	“xxx”	“xxx”	“xxx”	“xxx”	“xxx”	“xxx”
	“Response B”	“xxx”	“xxx”	“xxx”	“xxx”	“xxx”	“xxx”	“xxx”	“xxx”	“xxx”	“xxx”	“xxx”	“xxx”	“xxx”	“xxx”
	Missing	“xxx”	“xxx”	“xxx”	“xxx”	“xxx”	“xxx”	“xxx”	“xxx”	“xxx”	“xxx”	“xxx”	“xxx”	“xxx”	“xxx”
	Total	“xxx”	“xxx”	“xxx”	“xxx”	“xxx”	“xxx”	“xxx”	“xxx”	“xxx”	“xxx”	“xxx”	“xxx”	“xxx”	“xxx”
“Group Y2”	“Response A”	“xxx”	“xxx”	“xxx”	“xxx”	“xxx”	“xxx”	“xxx”	“xxx”	“xxx”	“xxx”	“xxx”	“xxx”	“xxx”	“xxx”
	“Response B”	“xxx”	“xxx”	“xxx”	“xxx”	“xxx”	“xxx”	“xxx”	“xxx”	“xxx”	“xxx”	“xxx”	“xxx”	“xxx”	“xxx”
	Missing	“xxx”	“xxx”	“xxx”	“xxx”	“xxx”	“xxx”	“xxx”	“xxx”	“xxx”	“xxx”	“xxx”	“xxx”	“xxx”	“xxx”
	Total	“xxx”	“xxx”	“xxx”	“xxx”	“xxx”	“xxx”	“xxx”	“xxx”	“xxx”	“xxx”	“xxx”	“xxx”	“xxx”	“xxx”
Total	“Total Response A”	“xxx”	“xxx”	“xxx”	“xxx”	“xxx”	“xxx”	“xxx”	“xxx”	“xxx”	“xxx”	“xxx”	“xxx”	“xxx”	“xxx”

“Total Response B”	“xxx”													
Missing	“xxx”													
Total	“xxx”													

Table 7.1.2: Grouped Frequencies Table Template

7.2. DESCRIPTIVE STATISTICS

Descriptive Statistic tables must contain the items listed in Table 7.2.1. Furthermore, the associated unit must be displayed. If the values are referring to a subgroup (n) and not to the overall population (N), a notification must be entered in the headline(“n = xxx”).

“Analysis Section” – “Variable Label” – Descriptive Statistics (n = “xxx”)

Characteristic		Arm A	Arm B	Total
		[“unit”]	[“unit”]	[“unit”]
“Variable Label”	Mean	“xxx”	“xxx”	“xxx”
	Median	“xxx”	“xxx”	“xxx”
	SD	“xxx”	“xxx”	“xxx”
	IQR	“xxx”	“xxx”	“xxx”
	Range	“xxx”	“xxx”	“xxx”
	Max	“xxx”	“xxx”	“xxx”
	Min	“xxx”	“xxx”	“xxx”

Table 7.2.1: Descriptive Statistics Table Template

